### 5.8. Analysis of Safety Data

The summary of safety results will be presented separately for the DBTP and SBTP, unless otherwise noted. Safety summaries for the DBTP will be presented by treatment group (ie, mibavademab, placebo) containing patients from the DB SAF. Safety summaries for the SBTP will be presented by all patients and by study treatment group in DBTP (ie, DB mibavademab, DB placebo), for patients in the SB SAF. No formal inferential testing will be performed for either period. Summaries will be descriptive in nature.

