Baseline testing occurs in the screening period and the placebo run-in period (see Table 1). After baseline testing, patients in each cohort will be randomized 1:1 to study arm 1 (placebo in TP1 and REGN4461 in TP2) or study arm 2 (REGN4461 in TP1 and TP2), and stratified based on screening HbA1c (HbA1c \leq 7.0% or HbA1c \geq 7.0%) within each cohort.

On day 1, the first dose will be administered IV (mg/kg REGN4461 or placebo) and patients will be observed for at least 4 hours. Starting on day 8, patients will receive matched volumes of SC administered REGN4461 (mg QW) or placebo, respectively, once weekly for a total of 11 SC doses. Fasting blood draws will be taken every 2 weeks according to Table 2.

During the final 2 weeks of TP1, fasting blood draws will be performed weekly (weeks 10, 11, 12). The mean (geometric for TG and arithmetic for all other measures) of these 3 measurements will be taken as the end measure of TP1 and beginning measurement for TP2. Bioimpedance will be assessed during a mandatory in-clinic study visit (week 12). At the end of TP1, patients will undergo liver MRI and whole-body DXA.

12-week single-blind treatment period (TP2); Day 85 until week 24

On day 85 (week 12), patients will receive double-blind dosing in order to maintain blinding to study arm assignment and will then be observed for at least 4 hours:

- Study arm 1: IV loading dose of REGN4461 (mg/kg) followed by SC placebo;
- Study arm 2: placebo IV infusion followed by SC REGN4461 (mg).

Starting at week 13, REGN4461 (mg SC QW) will be administered in a single-blind manner to patients in both study arms (patient remains blinded to treatment allocation). Fasting TG and glucose measurements will occur every 2 weeks through week 20 (Table 2). During the final 2 weeks of TP2, fasting blood draws will be performed weekly (weeks 22, 23, 24). The mean (geometric for TG and arithmetic for all other measures) of these 3 measurements will be taken as the end measure of TP2. Bioimpedance will be assessed during the mandatory in-clinic visit (week 24). At week 24, patients will undergo liver MRI and whole-body DXA.

16-week off-drug safety follow-up period; Day 169 until week 40

This period will be used to monitor efficacy (glycemic, lipid parameters, daily lipodystrophy hunger patient reported outcome [PRO]), safety (hematology, chemistry, urinalysis, vital signs and AEs), PK and PD assessments as REGN4461serum concentrations decline.

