## 2. INVESTIGATION PLAN

# 2.1. Study Design and Randomization

The study consists of the following 5 periods (Figure 1):

- A screening period up to 10-weeks
- A placebo run-in period (PBO) for 4 weeks
- A randomized double-blind placebo-controlled treatment period (TP1 or DBTP) for 12 weeks
- A single-blind treatment period (TP2 or SBTP) during which all patients receive mibavademab for 12 weeks
- An off-drug safety follow-up period for 16 weeks

Figure 1: Study Flow Diagram

Patients 18 years of age or older with a clinical diagnosis of FPLD will undergo screening, including measurement of HbA1c, fasting TG, and leptin levels. A diagnosis of FPLD requires either a documented ClinVar pathogenic or likely pathogenic variant in a known FPLD gene or pathognomonic regional lipoatrophy by DXA. In addition, patients must have metabolic abnormalities (elevated fasting TG with or without elevated HbA1c) and leptin level ≤20.0 ng/mL to be included.

After the screening period of up to 10 weeks, eligible patients will be assigned to one of the following two leptin cohorts based on the mean screening leptin levels:

Regeneron Pharmaceuticals, Inc.

Page 15 of 88

- Cohort A: FPLD patients with serum leptin <8.0 ng/mL
- Cohort B: FPLD patients with serum leptin 8.0 to ≤20.0 ng/mL

Then, these patients will begin the single-blind 4-week placebo run-in period.

On Day 1 after the placebo run-in period, each cohort of patients will be centrally randomized via interactive voice response system (IVRS) in a 1:1 ratio to Arm 1 or Arm 2:

- Arm 1: placebo
- Arm 2: mibayademab

Subjects will be stratified based on screening HbA1c (HbA1c  $\leq$ 7% or HbA1c  $\geq$ 7%) to ensure equal representation of patients with elevated HbA1c in each study arm. Schedules of study treatments and follow-up periods are summarized in Table 1.

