**Table 1: Summary of Study Arms** 

		Arm 1	Arm 2	
Double- blind	Day 1 (IV loading dose based on weight)	Placebo IV	mg/kg mibavademab IV	
Treatment Period (DBTP)	Day 8 onwards (for 11 weekly maintenance doses)	Placebo SC QW	mg mibavademab SC QW	
Single- blind Treatment Period (SBTP)	Day 85 (IV loading dose based on weight)	■ mg/kg mibavademab IV followed by Placebo SC	Placebo IV followed by mg mibavademab SC	
	Day 92 (for 11 weekly doses)	mg mibavademab SC QW		
	Day 169 until week 40	Off-Drug Safety Follow-up		

The study event table is presented in Appendix 10.7.

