# 4.6. Study Treatment Exposure and Compliance Variables

Study treatment exposure variables for study drug administered during the DBTP are listed below with associated definitions:

- Patient duration of DBTP SC study treatment exposure in weeks defined as: (last double-blind SC study treatment administration date first double-blind SC study treatment administration date+7)/7. Values will be rounded to one decimal place.
- The total number of DBTP SC study treatment injections by patient.
- The following categories will be used for DBTP SC treatment exposure at 1-week intervals: ≥1 day and <1 week, ≥1 week and <2 weeks, ≥2 weeks and <3 weeks, ≥3 weeks and <4 weeks, ..., ≥10 weeks and <11 weeks, ≥11 weeks.
- The total number of DBTP IV study treatment administrations by patient.

Study treatment exposure variables for study drug administered during the SBTP are listed below with associated definitions:

- Patient duration of SBTP SC study treatment exposure in weeks defined as: (last single-blind SC treatment administration date first single-blind SC treatment administration date+7)/7. Values will be rounded to one decimal place.
- The total number of SBTP SC study treatment injections by patient.
- The following categories will be used for SBTP SC treatment exposure at 1-week intervals: ≥1 day and <1 weeks, ≥1 weeks and <2 weeks, ≥2 weeks and <3 weeks, ≥3 weeks and <4 weeks, ..., ≥22weeks and <23 weeks, ≥23 weeks.
- The total number of SBTP IV study treatment administrations by patient.

Cumulative study treatment exposure variables combining DBTP and SBTP are listed below for all patients who received mibavademab in the DBTP:

- Cumulative patient duration of SC study treatment exposure in weeks defined as: DBTP SC treatment exposure + SBTP SC exposure.
- Cumulative total number of SC treatment administration by patient defined as: DBTP SC injections + SBTP SC injections.
- The following categories will be used for cumulative patient mibavademab treatment exposure in the study at 1-week intervals: ≥1 day and <1 weeks, ≥1 weeks and <2 weeks, ≥2 weeks and <3 weeks, ≥3 weeks and <4 weeks, ..., ≥22 weeks and <23 weeks, ≥23 weeks.
- The total number of DBTP and SBTP IV study treatment administrations by patient.

Regeneron Pharmaceuticals, Inc.

Page 23 of 88

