#### **5.8.3.** Adverse Events of Interest

Treatment emergent adverse events for mild infusion reactions, mild hypersensitivity reactions, and injection site reactions (ISR) as defined in Section 4.8.1.3 will be summarized by patient frequency (%) by SOC and PT.

Treatment emergent adverse events for infusion reactions and hypersensitivity reactions will also be summarized regardless of severity by SOC and PT.

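### Single-blind infusion reactions and IV counts are shown by prior arm and for all patients, never by the product infused on Day 85, when the two arms receive opposite products

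*SAP*

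**What the plan says.** **Day 85 treatment.** Protocol 6.1 gives the scheme (dose amounts are blacked out): "Study arm 1: IV loading dose of REGN4461 (mg/kg) followed by SC placebo" and "Study arm 2: placebo IV infusion followed by SC REGN4461". SAP Table 1 puts Day 85 in the single-blind period and shows the same for Arm 2: "Placebo IV followed by mg mibavademab SC". It schedules no other infusion in that period. SAP 2.1 nevertheless describes the period as one "during which all patients receive mibavademab for 12 weeks".

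**Safety tables.** SAP 5.8: "Safety summaries for the SBTP will be presented by all patients and by study treatment group in DBTP". The text then names the groups as DB mibavademab and DB placebo. Under SAP 4.8.1 the single-blind treatment-emergent period opens at the first single-blind administration, so a Day 85 infusion reaction falls in these tables. Under SAP 5.8.1 the percentage denominator is the safety set within each group. SAP 4.8.1.2 makes moderate or severe infusion reactions an adverse event of special interest (AESI), and SAP 5.8.3 adds: "Treatment emergent adverse events for infusion reactions and hypersensitivity reactions will also be summarized regardless of severity by SOC and PT". Protocol 10.2.4 defines an infusion reaction by timing alone, whichever product was infused.

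**Exposure.** SAP 5.6 presents SBTP exposure for all patients and by DB group. For patients who received mibavademab in the double-blind period (DBTP), the cumulative list in SAP 4.6 includes: "The total number of DBTP and SBTP IV study treatment administrations by patient". The cumulative summary in SAP 5.6.1 that is actually named for mibavademab covers SC dosing only.

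**The concern.** An infusion reaction is attributed to the infusion that preceded it, so its natural denominator is patients infused with that product. For this one event the SBTP columns run against the product. Every infusion under DB mibavademab is placebo, and every infusion under DB placebo is mibavademab. The all-patients column combines the two. Because SAP 2.1 describes the period as one in which everyone is on drug, a reader could easily take the all-patients figure for a drug rate.

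The mibavademab infusions are also split across two tables, one set under a placebo heading, and are never combined. At this sample size, combining them doubles the denominator for an AESI. The SAP already applies this principle to efficacy: its Table 5 re-aligns both arms to the first active dose. Safety has no counterpart.

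The study ended early with limited enrolment (SAP 1.2.4). That section restricts the efficacy analyses to descriptive summaries, but the safety tables remain planned. With few patients, one event read under the wrong product changes a percentage visibly.

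**Working it through.** **Inputs.** 10 patients per arm per cohort and two cohorts (Protocol 6.1.1), so 20 per arm. Products by day come from Protocol 6.1 and 8.1 and SAP Table 1. Dosing days come from the schedule of events. The documents give no infusion-reaction rate, so the rates below are assumptions shown over a range.

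**1. The plan's own figure.** SC visits run weekly from Day 8 to Day 78 in the DBTP and from Day 85 to Day 162 in the SBTP.

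- DBTP SC doses: (78 − 8)/7 + 1 = 11
- SBTP SC doses: (162 − 85)/7 + 1 = 12
- Duration by the SAP 4.6 formula: (78 − 8 + 7)/7 = 11.0 weeks and (162 − 85 + 7)/7 = 12.0 weeks, 23.0 weeks in total

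This matches the top cumulative category in SAP 4.6 (23 weeks or more). Counting the Day 85 injection as an SBTP dose is therefore consistent with the SAP.

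**2. Infusions by product at planned size, if everyone enters the SBTP.**

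| Infusion | Table column | Patients | Product infused |
|---|---|---|---|
| Arm 1, Day 1 | DBTP placebo | 20 | placebo |
| Arm 2, Day 1 | DBTP mibavademab | 20 | mibavademab |
| Arm 1, Day 85 | SBTP DB placebo | 20 | mibavademab |
| Arm 2, Day 85 | SBTP DB mibavademab | 20 | placebo |
| Both arms, Day 85 | SBTP all patients | 40 | 20 mibavademab, 20 placebo |

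**3. What the all-patients column shows.** With n₁ patients infused with drug at rate r_m and n₂ with placebo at rate r_p:

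shown rate = (n₁ × r_m + n₂ × r_p)/(n₁ + n₂)

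With n₁ = n₂ = 20:

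| Assumed drug rate | Shown if placebo rate is 0% | Shown if placebo rate is 5% |
|---|---|---|
| 5% | 2.5% | 5.0% |
| 10% | 5.0% | 7.5% |
| 20% | 10.0% | 12.5% |
| 30% | 15.0% | 17.5% |

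With no placebo reactions the column shows exactly half the drug rate. With unequal arms the factor is n₁/(n₁ + n₂).

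**4. What pooling adds.** Mibavademab infusions: 20 (Arm 2, Day 1) + 20 (Arm 1, Day 85) = 40 patients, each infused with drug once. With zero events the exact one-sided 95% upper bound is 1 − 0.05^(1/n), which is 13.9% for n = 20 and 7.2% for n = 40.

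**5. Exposure counts per patient who completes dosing.**

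| Count | Total study treatment | Of which mibavademab |
|---|---|---|
| Arm 2 cumulative IV | 1 + 1 = 2 | 1 |
| Arm 1 SBTP SC | 12 | 12 − 1 = 11 |
| Arm 2 cumulative SC | 11 + 12 = 23 | 23 |

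**The case against.** Three stronger readings are tempting, and the documents support none of them.

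- **That no planned table gives a reaction rate for mibavademab infusions.** Each patient has one infusion per period, so the percentage of patients is the rate per infusion. The DBTP mibavademab column and the SBTP DB placebo column each give a clean active-infusion rate with the right denominator. What is missing is a label saying so and a pooled figure.
- **That placebo infusions contaminate a figure the SAP calls a mibavademab rate.** The SBTP columns are named for the earlier randomized group and for all patients. The SAP nowhere calls the all-patients figure a mibavademab rate; that reading comes only from the general description of the period.
- **That drug exposure is overstated.** The IV item counts study-treatment administrations, and 2 is a correct count of those. The summary named for mibavademab is SC only and is correct for Arm 2. Arm 1's Day 85 placebo injection never enters it.

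It is also fair to say that safety is descriptive, that Protocol 10.1.2 requires a detailed narrative for each AESI, and that the table of 40 patients will not occur as planned after early termination.

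A further point limits the remedy. On Day 85, Arm 2 has already had the double-blind course of mibavademab and receives it SC after the placebo infusion. The reaction window extends two hours beyond the end of the infusion, and no interval between the IV and SC doses is stated. An event in that window may not be a clean placebo event.

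All of this stands. It reduces the point to labelling, one mixed column and a missing pooled rate. It does not remove it.

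**Conclusion.** The point holds as a reporting defect that should be corrected. No arm-level rate and no mibavademab-labelled SC total is wrong. Four things are deficient:

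- The SBTP arm labels run opposite to the product infused.
- The all-patients column for an AESI mixes drug and placebo infusions equally at planned size.
- No table pools the mibavademab infusions.
- Arm 2's cumulative IV count (2, of which 1 is drug) and Arm 1's SBTP SC count (12, of which 11 are drug) do not show how much was drug.

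The halving of the rate assumes equal numbers entering the SBTP and no reactions to placebo infusions. Actual enrolment is below plan and is not given in the documents, so the real mix may differ. The reversal of labels does not depend on numbers at all.

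**What to change.** In SAP 5.6.1, 5.8.2 and 5.8.3:

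- Add one tabulation of infusion reactions and IV counts by product actually infused. Mibavademab is Arm 2 Day 1 plus Arm 1 Day 85, shown pooled.
- In that table, show the placebo infusions in two separate groups, Arm 1 Day 1 and Arm 2 Day 85. They should not be merged, because Arm 2 is already exposed to mibavademab and receives it SC that day.
- Keep the existing arm columns and the all-patients column. Footnote each SBTP column, including all patients, with the product infused on Day 85.
- Report mibavademab administrations separately from total study-treatment administrations: 1 of 2 for Arm 2 cumulative IV and 11 of 12 for Arm 1 SBTP SC under full dosing.

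The cost is one extra table, some footnotes and limited reprogramming. The data are already collected.

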#### General common rules

All safety analyses will be performed, unless otherwise specified, using the following common rules:

- Safety data in patients who do not belong to the safety analysis sets (ie, exposed but not randomized) will be listed separately.
- Potentially Clinically Significant Values (PCSVs) or Potentially Clinically Significant Abnormalities (PCSAs) are defined as abnormal values considered medically important by the Sponsor according to predefined criteria/thresholds based on literature review and defined by the Sponsor for clinical laboratory tests, vital signs, ECG (PCSV version dated January 2009 [Appendix 10.4]).

Regeneron Pharmaceuticals, Inc.

Page 42 of 88

Protocol: R4461-PLD-20100

• PCSV criteria will determine which patients had at least 1 PCSV during the respective TEAE period, taking into account all evaluations including unscheduled or repeated evaluations.

Protocol: R4461-PLD-20100

Date: May 16, 2024

- The treatment-emergent PCSV denominator for a given parameter will be based on the number of patients assessed for that given parameter at least once during the respective TEAE period.
- All measurements, scheduled or unscheduled, fasting or not fasting, will be assigned
  to the Global Analysis Windows defined in Appendix 10.2 to provide an assessment
  for the screening visit through follow-up visit time points.
- For quantitative safety parameters including central laboratory measurements and vital sign scores, descriptive statistics will be used to summarize observed values and change from baseline values by visit.
- Unless otherwise specified, in the case of multiple assessments within an analysis
  window, the assessment closest to the protocol planned visit study day will be used in
  analysis.

#### **5.8.1.** Adverse Events

In general, the primary focus of AE reporting will be on TEAEs summarized in respective TEAE period, specifically the DBTP and SBTP.

If an AE onset date (occurrence, worsening, or becoming serious) is incomplete, an imputation algorithm will be used to classify the AE as pre-treatment, treatment-emergent, or post-treatment. The algorithm for imputing date of onset will be conservative and will classify an AE as treatment-emergent unless there is definitive information to determine pre-treatment or post-treatment status. Details on classification of AEs with missing or partial onset dates are provided in Section 6.3.

Adverse event incidence tables will present the number (n) and percentage (%) of patients experiencing an AE by SOC and PT. In addition, incidence tables by SOC and PT will be provided for all TEAEs, serious TEAEs, and TEAEs leading to permanent treatment discontinuation. Multiple occurrences of the same event in the same patient will be counted only once in the tables. For tables presenting severity of events, the worst severity will be chosen for patients with multiple instances of the same event. The denominator for computation of percentages is the respective safety analysis set within each treatment group.

AE incidence tables will present data by SOC and PT and summarize the number (n) and percentage (%) of patients experiencing an AE.

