# 2.2. Justification of Sample Size

The size of the study is determined by feasibility assessments. Due to the limited number of identified FPLD patients with low leptin and moderate metabolic abnormalities, up to 40 patients will be enrolled.

With a total of 40 patients (20 per cohort, randomized in the ratio of 1:1 into Arm 1 and Arm 2), the primary analysis will be carried out on the 20 patients in the lower leptin Cohort A in DBTP. The fact that it is unlikely that all of the patients will have HbA1c >7.0%, ie, not all of the patients will be assessed for the HbA1c endpoint, has also been accounted for. From the feasibility work, it is estimated that 78% of the patients will have elevated screening HbA1c. With 20 patients in Cohort A (10 patients per study arm; Table 2), the half-width of the 90% confidence interval of the difference in change from baseline to week 12 between Arm 1 and Arm 2 for HbA1c is 1.4 percentage points, assuming a SD of 1.81%. For TG, the half-width of the 90% confidence interval

Regeneron Pharmaceuticals, Inc.

Page 16 of 88

Protocol: R4461-PLD-20100

in logarithm-transformed geometric mean ratio (GMR) (mibavademab week12/baseline divided by placebo week12/baseline) is 0.67, assuming the SD for logarithm-transformed fasting TG is 0.87. The SD estimates are from the FPLD subset samples of the extracted NIH study data (Diker-Cohen. 2015).

Table 2: Half-Width of the 90% Confidence Interval for Primary Endpoints

Endpoint	Number of Patients per Group in the Subset	Half of the 90% confidence interval**	
HbA1c*	7	1.72%	
	8	1.59%	
HbA1c †	10	1.4%	
Fasting TG †	10	0.67	

\*Assuming 78% of the patients have elevated screening HbA1c.

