# 3.2. Safety Analysis Sets (SAF)

## 3.2.1. Double-Blind Safety Analysis Set

The double-blind safety analysis set (DB SAF) includes all randomized patients who received any double-blind study drug. Patients will be analyzed according to the treatment received (as treated). Treatment compliance/administration and all clinical safety variables will be analyzed using the double-blind SAF.

Regeneron Pharmaceuticals, Inc.

Page 17 of 88

Protocol: R4461-PLD-20100

\*\*The estimates of treatment effects of drug at the end of the DBTP (week 12) are -1.18% for HbA1c, and -52% for fasting TG. After adjusting for placebo effect, the between-group treatment effect estimates are -0.98% for HbA1c, and -47% for fasting TG. SD for HbA1c is assumed to be 1.81%, and for logarithm-transformed fasting TG is assumed to be 0.87 (SD estimates extracted from NIH study data).

<sup>†Assuming all patients have baseline HbA1c >7.0% and TG >200 mg/dL.

In addition:

• Randomized patients for whom it is unclear whether they took the study drug will be included in the DB SAF as randomized.

Protocol: R4461-PLD-20100

Date: May 16, 2024

• For randomized patients receiving both mibavademab and placebo study treatment in the DBTP, the treatment group allocation for as-treated analysis will be mibavademab.

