#### The AESIs include:

- Hypoglycemia, defined as blood glucose <54 mg/dL (eCRF, lab data)
- New onset diabetes mellitus (NODM) (eCRF, lab data)
- For patients with no diabetes at baseline, NODM is defined using the following lab parameters:
  - a. Two values of fasting ( $\geq 8$  hours) plasma glucose  $\geq 126$  mg/dL (7.0 mmol) during the treatment period

OR

- b. Two values of HbA1c ≥6.5% (48 mmol/mol) during the treatment period
- Hyperglycemia requiring treatment (eCRF, lab data), defined using the following lab parameter:
  - a. HbA1c ≥10.5% AND at the same visit an increase in HbA1c of ≥1.5% from baseline value

OR

- b. Fasting glucose ≥250 mg/dL on 2 occasions including symptoms consistent with hyperglycemia AND increase in fasting glucose >50 mg/dL above baseline
- Development of new or worsening of autoimmune disease (eCRF)
- Moderate or severe hypersensitivity reactions (CMQ, eCRF)
- Moderate or severe infusion reactions (eCRF)

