#### **5.8.2.** Analysis of Adverse Events of Special Interest

Treatment-emergent adverse events of special interest (AESI), as listed in Section 4.8.1.2, will be presented by SOC and PT as applicable. AESI are defined by SMQ, CMQ, lab data, and/or dedicated e-CRF are summarized by frequency (%) as described in Appendix 10.3.

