### 10.3. List of AESIs with Data Sources and Definitions of SMQ/CMQ

Table 19: Summary of AESIs and the Methods of Data Collections and Derivations

AESI	Using an e-CRF specific tick box on AE page	Using Standard MedDRA Query (SMQ)/company MedDRA Query (CMQ) or Laboratory data criteria
Hypoglycemia	Yes	Blood glucose <54 mg/dL
New onset diabetes mellitus (NODM)	Yes	For patients with no diabetes at baseline:
		• Two values of fasting (≥8 hr) plasma glucose ≥126 mg/dL (7.0 mmol) during treatment period
		OR
		• Two values of HbA1c ≥6.5% (48 mmol/mol) during treatment period
		Note: Patients who meet either of these criteria during the PBO run- in period will be considered to have diabetes at baseline.
Hyperglycemia requiring treatment	Yes	HbA1c ≥10.5% AND increase in HbA1c of ≥1.5% from baseline value OR b. Fasting glucose ≥250 mg/dL on 2 occasions AND increase in fasting glucose >50 mg/dL above baseline
Development of new or worsening of autoimmune disease	Yes	N/A
Moderate and severe Hypersensitivity reactions	Yes	CMQ 'Hypersensitivity, which is defined as Hypersensitivity SMQ (narrow) excluding the following PTs:

Protocol: R4461-PLD-20100

		0	Injection site
			dermatitis,
		0	Injection site eczema,
			Injection site
			hypersensitivity,
		0	Injections site rash,
		_	•
		0	injection site reaction,
		0	Injection site recall
			reaction,
		0	Injection site urticaria,
		0	Injection site vasculitis
Moderate and severe	Yes	N/A	
infusion reactions	105	14/11	
iniusion reactions			

^ dedicated CRF for ISR captures event PT and associated symptoms

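### The SAP sets no at-risk denominator for new-onset diabetes, so as written its percentage is taken over the whole safety set, including patients who already have diabetes, and understates incidence among those at risk

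*SAP*

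**What the plan says.** SAP 5.8.1 closes its paragraph on adverse event incidence tables with "The denominator for computation of percentages is the respective safety analysis set within each treatment group". The double-blind set is not restricted by diabetes status: "The double-blind safety analysis set (DB SAF) includes all randomized patients who received any double-blind study drug" (SAP 3.2.1). The single-blind set is likewise every randomized patient who received single-blind drug (SAP 3.2.2).

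SAP 5.8.2 covers the events of special interest and says they "are summarized by frequency (%) as described in Appendix 10.3". It names no denominator of its own.

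The event is confined to a subgroup. SAP 4.8.1.2 reads "For patients with no diabetes at baseline, NODM is defined using the following lab parameters", and one of the two criteria is "Two values of HbA1c ≥6.5% (48 mmol/mol) during the treatment period"; the other is two fasting glucose values of at least 126 mg/dL. The NODM row of Table 19 (Appendix 10.3) opens with "For patients with no diabetes at baseline". Table 19 and Protocol 10.1.3 add that anyone who meets either criterion in the placebo run-in is treated as diabetic at baseline.

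On case mix, SAP 2.2 states that "it is estimated that 78% of the patients will have elevated screening HbA1c", where elevated means above 7.0%.

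**The concern.** The numerator and the denominator describe different populations. A patient who has diabetes at baseline can never be a case of NODM but is counted in the divisor. This population is expected to be mostly hyperglycaemic, so most of the divisor could be made up of such patients. The printed percentage would then be a small fraction of the incidence in the people to whom the event can happen.

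The single-blind table adds a second layer. Its event period starts at the first single-blind dose (SAP 4.8.1), and its set keeps patients who already met NODM in the double-blind period, although a new onset is no longer possible for them.

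NODM is one of the events that must reach the sponsor within 24 hours (Protocol 10.1.3) and is named in the risk-benefit discussion (Protocol 3.3.1). A reader of the report will take its percentage as a statement of risk. Other tables do not reliably give back the number at risk:

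- Baseline summaries split HbA1c at 7.0%, not by diabetes status (SAP 5.1).
- Medical history would not show patients reclassified in the run-in (SAP 5.2).
- The hyperglycaemia criteria for potentially clinically significant values use much higher thresholds: fasting glucose of at least 250 mg/dL with a rise above 50 mg/dL, or HbA1c of at least 10.5% with a rise of at least 1.5% (Table 20).

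**Working it through.** **The plan's own figures.** The documents state no NODM rate and no number at risk. The nearest check is whether the 78% is the case mix the plan really uses. The 90% half-width is t(0.95, 2n−2) × SD × √(2/n).

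| Endpoint | n per group | SD | Computed | SAP Table 2 |
|---|---|---|---|---|
| HbA1c | 7 | 1.81 | 1.724 | 1.72 |
| HbA1c | 8 | 1.81 | 1.594 | 1.59 |
| HbA1c | 10 | 1.81 | 1.404 | 1.4 |
| Log TG | 10 | 0.87 | 0.675 | 0.67 |

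The table reproduces. Since 0.78 × 10 = 7.8, the rows at 7 and 8 per group are the 78% subset of a cohort A arm.

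**Dilution factor.** With N patients in the safety set and R of them at risk, the same cases give a percentage N/R times larger over R than over N. If every patient with HbA1c above 7.0% is diabetic at baseline and no one else is, R/N = 1 − 0.78 = 0.22 and N/R = 1/0.22 = 4.55.

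At the planning size of 20 per arm over both cohorts, R = 0.22 × 20 = 4.4. In whole patients:

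- 15 of 20 above 7.0% leaves 5 at risk. One case is 1/20 = 5% of the safety set and 1/5 = 20% of those at risk, a factor of 4.0.
- 16 of 20 above 7.0% leaves 4 at risk. One case is 5% against 1/4 = 25%, a factor of 5.0.

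**Sensitivity to classification.** Let q be the share of patients at or below 7.0% who are nevertheless diabetic (HbA1c from 6.5% to 7.0%, or treated diabetes). Let u be the share above 7.0% who are not classed as diabetic at baseline. The factor is 1 / [0.22(1 − q) + 0.78u]. The values of q and u are assumptions; the documents give neither.

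| q | u = 0 | u = 0.05 | u = 0.10 |
|---|---|---|---|
| 0 | 4.55 | 3.86 | 3.36 |
| 0.25 | 6.06 | 4.90 | 4.12 |
| 0.50 | 9.09 | 6.71 | 5.32 |

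The range is about 3.4 to 9. A non-zero u is possible because the run-in criterion needs two values, while Protocol Table 1 schedules one HbA1c in the run-in (fasting glucose is scheduled four times), and neither document fully defines absence of diabetes at baseline.

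**Between arms.** The ratio of safety-set percentages equals the ratio of at-risk percentages when the arms have the same share at risk. With 4 of 20 at risk in one arm and 5 of 20 in the other, and one case in each, the safety-set percentages are 5% and 5% (ratio 1.0), and the at-risk percentages are 25% and 20% (ratio 1.25).

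**The case against.** **The denominator is inferred.** The sentence in SAP 5.8.1 belongs to a paragraph on tables by system organ class and preferred term, while events of special interest have their own section pointing to Appendix 10.3, whose NODM row begins with the no-diabetes condition. A programmer might read that as the analysed subset. Laboratory flags elsewhere in the SAP also have a parameter-specific denominator (SAP 5.8, general rules). This stands in part: the text can be misread either way. But the Table 19 column lists data sources and criteria, so the condition there defines a case, and 5.8.1 remains the only adverse event denominator given.

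**The size is not a floor.** A reader might infer that the rate is understated at least 4.5-fold. The documents do not support that. The 78% is a feasibility estimate of HbA1c above 7.0%, given in the cohort A sample-size paragraph; it is not a diabetes prevalence, and the sensitivity table includes values below 4.5. The arms of 20 are also planning sizes: SAP 1.2.4 says the study ended early with limited enrolment. This objection stands.

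**A signal is not hidden.** A reader might infer that cases would be lost from view. They would not: tables show counts as well as percentages, each case goes to the sponsor within 24 hours, and individual HbA1c and glucose plots are planned where applicable.

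**The arm comparison is largely protected.** A reader might infer that the arm percentages mainly reflect how many diabetic patients each arm holds. Randomization is stratified by screening HbA1c at 7.0% within each cohort (Protocol 8.6), so shares at risk should be similar on average. What remains is chance imbalance among few patients, and stratification does not balance diabetes status within the stratum at or below 7.0%.

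**Cases over all treated patients is a valid proportion.** So it is, but it answers a different question from incidence in those who can develop the condition, and the plan does not tell the reader which is shown.

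**Conclusion.** The point holds as a defect in reporting absolute incidence. As written, NODM is divided by a set that includes patients excluded from the event by definition, and nothing in SAP 5.8.2 or Appendix 10.3 changes that.

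On the planned case mix the percentage understates at-risk incidence severalfold: about 4.5-fold as an illustration. This rests on three assumptions: the 78% applies to both cohorts, all patients above 7.0% count as diabetic at baseline, and the 5.8.1 rule governs the special-interest table. The actual factor depends on the patients enrolled before termination. No size can be given for the single-blind carry-over.

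The documents do not support a claim of concealed cases or a materially biased arm comparison. Early termination does not make the point moot: SAP 1.2.4 reduces the efficacy analyses to descriptive summaries but leaves the safety tables in place.

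**What to change.** In SAP 5.8.2 and the NODM row of Table 19, add a sentence to this effect: *the NODM percentage uses as denominator the patients in the respective safety analysis set who have no diabetes at baseline, applying the run-in rule, and, for the single-blind period, no NODM before the first single-blind dose; the table shows n/N at risk by arm.* State how the baseline flag is derived (for example, diabetes history plus the run-in criteria). Keep the safety-set denominator for the other events of special interest.

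The cost is one sentence and a baseline flag that is already needed to derive the event, plus a check for earlier NODM in the single-blind table. No new data and no clinical change are needed. The downside is a small denominator, giving an imprecise and less favourable-looking percentage; showing n/N lets the reader judge that.
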